5.2 Trial Treatment Plan

The treatment to be used in this trial is outlined below in **Table 2**

Table 2 Trial Treatment

Treatment	Dose	Frequency	Route	Use
MK-3475	200 mg*	Every 3 weeks (\pm 7 days)	IV infusion	Experimental
SBRT	30Gy **	One time over 1 to 5 fractions		Standard

*MK-3475 may be modified as described in Section 5.2.1

**SBRT dose escalated/de-escalated as described in Section 5.2.2

5.2.1 Study Design

This is a two-part study, including both phase 1b and 2a portions.

The **phase 1b** is an SBRT dose escalation study, in which patients with both NSCLC and melanoma will be enrolled. NSCLC patients will be enrolled and treated with MK-3475 until they have progression of disease (irPD). Patients who have progression within 12 months of study entry will be evaluated for SBRT and re-initiation of MK-3475. Patients who do not have progression of disease within that timeframe may continue to receive MK-3475 for up to 18 months per protocol. These patients will not be evaluable for the study endpoints, although their response rates and overall survival will be reported.

Melanoma and selected NSCLC patients will be enrolled after having progression of disease on prior PD-1 therapy (irPD). They will be immediately treated with SBRT, followed by re-initiation of MK-3475.

After progression of disease on an initial course of anti-PD-1 therapy (either prior to enrollment, or during trial therapy), a target for SBRT will be selected and patients will be assigned to one of two arms on the basis of the anatomic location of the target (Arm A: lung, Arm B: non-lung). The SBRT target will be chosen and ideally SBRT will be delivered as quickly as feasible after the last infusion of MK-3475. NSCLC patients who do not have a suitable SBRT target (as defined in section 5.2.3) on the imaging study that shows progression of disease may undergo interval re-imaging without further therapy, but if no suitable target has been identified for SBRT within 12 weeks of the last infusion of MK-3475, that patient will be removed from treatment and moved to survival follow up.

Patients may continue to receive MK-3475 post disease progression while radiation therapy with SBRT is scheduled. Patients who require continuing corticosteroid treatment, or who have adverse events (grade 3 or greater non-hematologic, or grade 2 pneumonitis) due to MK-3475 that do not resolve within 12 weeks of AE start date will not receive SBRT and will also be removed from study. Patients who develop grade 3 pneumonitis will be removed from the study, regardless of whether it resolves. SBRT will be delivered in dose cohorts as described below in section 5.3.

Following SBRT, all patients will restart MK-3475 as soon as feasible. They will continue until they have further progression of disease, defined as irPD, or at the discretion of the treating physician if they are felt to receiving clinical benefit.

If MK-3475 is held at any point during a subject's participation in the trial for any reason, the subject will be followed as per standard of care until treatment with MK-3475 is resumed. When treatment with MK-3475 is resumed, the subject will continue with Day 1 procedures for the next planned cycle.

The **phase 2a portion** is an expansion cohort with enrollment closing when 20 NSCLC patients have been enrolled (including those enrolled on phase I). Similar to the phase Ib portion, NSCLC patients who initiated trial therapy on MK-3475 will receive MK-3475 until there is progression of disease (irPD). Patients who do not have progression of disease within that timeframe may continue to receive MK-3475 for up to 18 months per protocol. These patients will not be evaluable for the study endpoints, although their response rates and overall survival will be reported. NSCLC patients will be enrolled after they have irPD on anti-PD-1 therapy received prior to study entry. After progression, an SBRT target will be selected and patients will be treated at the SBRT MTD as determined in the Phase Ib portion of the study, for lung and non-lung targets. The SBRT target will be chosen and ideally SBRT will be delivered as quickly as feasible after the last infusion of MK-3475. In the event of drug-related toxicity or other delay, SBRT may start up to 12 weeks after the last infusion as detailed below in section 5.2.3. Following SBRT, all patients will receive MK-3475 until they develop progression of disease (as defined by irPD), or until they are no longer receiving clinical benefit.

For each phase of the study, the first course of MK-3475 will start on day 1, and will be given every 3 weeks (+/- 7 days) (one cycle). Patients will undergo re-imaging CT of the chest, abdomen, and pelvis at the end of cycle 2, cycle 4, and every 4 cycles thereafter (i.e., at cycles 8, 12, etc.). After the SBRT, when MK-3475 is re-initiated, imaging will be done at the end of cycles 2, 4, and then every 4 cycles. Exceptions to the timing of re-imaging can be made by the treating investigator as necessary to determine course of treatment.

Following SBRT, MK-3475 will be re-started and administered in 3-week cycles as quickly as feasible. Dose modifications or delays may be made per section 5.2.2, based on prior toxicity from the first course of drug treatment. Treatment will continue until progression of disease, which **will be defined for this purpose as progression in comparison to the tumor imaging obtained immediately before or after SBRT (whichever is more recent)**. At the discretion of the principal investigator, patients may continue to receive treatment if they are receiving clinical benefit. For the purpose of measuring response, the irradiated lesion will no longer qualify as measurable disease.

Progression of Disease (irPD) for this study will be defined using the Immune-Related Response Criteria (irRC), with the following qualification:

Radiographic progression of disease by RECIST criteria (but not by irRC) where, in the opinion of the investigator, the patient would no longer benefit from continuing drug therapy, will be considered progression of disease.

During the **pre-SBRT** MK-3475, radiation to isolated sites of metastatic disease is not permitted.

During the **post-SBRT** MK-3475, local surgery and/or radiation therapy to isolated sites of metastatic disease is permitted and the patient can continue the MK-3475 provided there is evidence of continuing benefit from systemic treatment (i.e., stable disease or response in at least one other measurable lesion, or clinical improvement).

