The first fraction of SBRT should be delivered as soon as feasible after progression of disease. For the following events, SBRT should be delayed until they resolve (for toxicities, to grade 0 or 1), up to 12 weeks after the last infusion of MK-3475. If the listed events do not resolve within 12 weeks of the last infusion of MK-3475, the patient will be removed from the study and replaced.

1. Grade 2 or greater pneumonitis
2. Corticosteroid use within 2 weeks of SBRT, except in individual cases allowed by the Principal Investigator
3. Grade 3 or greater non-hematologic toxicity related to study therapy

Patients who develop grade 3 or greater pneumonitis during the pre-SBRT MK-3475 will be taken off of the study, and will not be eligible for SBRT, or re-initiation of MK-3475.

Patients will be treated on non-consecutive days whenever possible, with all fractions to be scheduled within 15 calendar days from first to last. Localization of the tumor target before each fraction is required, by either cone-beam CT scan, kilovoltage on -board imaging, or an internal fiducial.

SBRT Dose Modification and Supportive Care

SBRT will be discontinued if any grade 3 or greater adverse event occurs during radiation treatment that is probably or definitely attributable to radiation. This will be counted as a DLT if it occurs during the phase Ib portion of the study. These patients will be allowed to continue with trial therapy (the second course of MK-3475, but not the remainder of their SBRT) if the toxicity resolves to grade 0 or 1 with supportive measures within 12 weeks of AE start date.

SBRT will also be discontinued if the completion of all fractions is prolonged beyond 30 days for reasons unrelated to toxicity (i.e., intercurrent illness, or patient refusal). This will not be counted as a DLT, and these patients will be allowed to continue with trial therapy (the second course of MK-3475, but not the remainder of their SBRT) as long as the investigator believes that they will be compliant with the remainder of the trial therapy. In the phase Ib portion of the study, these patients will not be counted towards the minimum number of patient treated at that dose level as long as they have not experienced a DLT before treatment is abort, but instead will be replaced. If they have experienced a DLT during that period, then they will be counted toward that dose cohort.

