5.7 Subject Withdrawal/Discontinuation Criteria

Subjects may withdraw consent at any time for any reason or be dropped from the trial at the discretion of the investigator should any untoward effect occur. In addition, a subject may be withdrawn by the investigator if enrollment into the trial is inappropriate, the trial plan is violated, or for administrative and/or other safety reasons. Specific details regarding discontinuation or withdrawal are provided in Section 7.

A subject must be discontinued from treatment, or removed from the study for any of the following reasons:

- The subject or legal representative (such as a parent or legal guardian) withdraws consent.
- Progression of disease during the second course of MK-3475 (as defined in section 5.2.1)
- Unacceptable adverse experiences as described in Section 5.2
- Intercurrent illness that prevents further administration of treatment
- Investigator's decision to withdraw the subject
- The subject has a confirmed positive serum pregnancy test

- Noncompliance with trial treatment or procedure requirements
- The subject is lost to follow-up
- Completed 12 months of treatment with post-SBRT MK-3475
Note: 12 months of study medication is calculated from the date of first dose of the second course. Subjects who stop MK-3475 after 12 months will be eligible for up to one year of additional study treatment if they progress after stopping study treatment
- Administrative reasons

The End of Treatment and Follow-up visit procedures are listed in Sections 6 and 7. After the end of treatment, each subject will be followed for 30 days for adverse event monitoring (serious adverse events will be collected for 90 days after the end of treatment as described in Section 8). Subjects who discontinue treatment will be followed for survival until death, withdrawal of consent, or the end of the study, whichever occurs first. Survival follow up may be a phone call only.

58 Subject Replacement Strategy

In both phases of the study, patients will be replaced if

1. They do not complete at least one fraction of SBRT.
2. They do not complete their entire course of SBRT as prescribed due to reasons other than toxicity (e.g., patient refusal, or intercurrent illness).

59 Clinical Criteria for Early Trial Termination

Early trial termination will be the result of the criteria specified below:

1. Quality or quantity of data recording is inaccurate or incomplete
2. Poor adherence to protocol and regulatory requirements

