9.0 STATISTICAL ANALYSIS PLAN

In the phase 1b portion of the trial, patients will be enrolled in parallel dose escalation cohorts using the “Rolling Six” method, as described in Section 5.

The primary endpoint of the phase 2a portion of the study is the response rate to post-SBRT MK-3475, separately determined for a NSCLC cohort. A total of 12 patients will be treated at the MTD in the first phase of the study (6 each of lung and non-lung SBRT

targets), and we project that this will include an approximately equal number of NSCLC and melanoma patients. In the second phase of the study, an expansion cohort will be enrolled until a total of 20 NSCLC patients eligible to undergo SBRT is reached (including NSCLC patients treated in the phase I and II portions of the study). We project that approximately 30% of patients (unselected for PD-L1 expression) will respond to the initial MK-3475 for 12 months or more and be replaced. Of those who go on to progress and be SBRT, we estimate that 30% will drop out, or otherwise be ineligible for assessment of response to post-SBRT MK-3475.

There is no published data to suggest a historical control for response to re-treatment with MK-3475, in patients who have been previously treated with MK-3475 and have prior documented progression of disease. In melanoma patients treated with anti-CTLA4 antibody, there is a documented response rate for re-treatment of patients who previously responded and subsequently progressed. In a series of 31 patients who initially had a partial or complete response, and then had progression of disease, re-induction with antibody resulted in a response in 13% of patients. It should be noted, however, that treatment beyond standard RECIST criteria was not permitted in the initial treatment course for these patients, so some may have had pseudoprogression. It is therefore presumed that the expected ORR without SBRT in this population, allowing for treatment beyond RECIST in their initial therapy with MK-3475 is less than 5%. If 4 of 20 patients (20%) in the NSCLC expansion cohort develop a partial or complete response to post-SBRT MK-3475, this strategy will be deemed worth of further investigation. The 95% confidence interval will be (0.05, 0.49) by using one-sample proportion test with continuity correction.

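### Section 5.2.1 closes NSCLC accrual at 20 patients enrolled and Section 9.0 at 20 eligible for SBRT; followed literally, 5.2.1 could leave about 14 to 20 patients reaching SBRT for a rule written as 4 of 20

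*Combined protocol and SAP*

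**What the plan says.** **Closing rules.** Section 5.2.1 (phase 2a portion) calls this part of the trial an "expansion cohort with enrollment closing when 20 NSCLC patients have been enrolled (including those enrolled on phase I". Section 9.0 says that "an expansion cohort will be enrolled until a total of 20 NSCLC patients eligible to undergo SBRT is reached", again counting phase 1 patients. Section 9.0 adds that about 30% of patients are expected to respond to the initial MK-3475 for 12 months or more and to be replaced. Section 5.2.1 calls such patients not evaluable for the endpoints, but its closing count does not exclude them.

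**Later loss.** Section 9.0 expects a further 30% of those who go on to progress and receive SBRT to drop out or not be assessable for response.

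**Decision rule.** Section 9.0 deems the strategy worth pursuing if 4 of 20 NSCLC patients (20%) respond after SBRT. The presumed rate without SBRT is below 5%.

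**Replacement.** Section 5.8 opens with "In both phases of the study, patients will be replaced if" and gives two conditions: "They do not complete at least one fraction of SBRT", and "They do not complete their entire course of SBRT as prescribed due to reasons other than toxicity", with refusal and intercurrent illness as examples. Section 5.2.3 covers SBRT prolonged beyond 30 days for reasons unrelated to toxicity. It states replacement for phase 1b only, and keeps the patient in the dose cohort if a DLT has occurred. It also allows these patients to go on to the second MK-3475 course if the investigator expects them to comply.

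**The concern.** Being enrolled and being eligible for SBRT are different states for an NSCLC patient without prior anti-PD-1 therapy. Such a patient enrols, starts MK-3475, and becomes a candidate for SBRT only on progression within 12 months. A site that follows 5.2.1 closes accrual at the twentieth enrolment, and a patient who never reaches SBRT then cannot be replaced. The primary endpoint is response to MK-3475 after SBRT, so the rule of 4 of 20 would be applied to fewer than 20 SBRT patients.

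The second issue is the denominator. No section defines the analysis set for the response rate, or says whether a phase 2a patient who starts SBRT and is replaced under 5.8 is still counted. If such patients are dropped and tend not to respond, the reported rate is too high.

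**Working it through.** **The plan's own figures.** 4/20 = 20% is correct. The 95% interval given for it in Section 9.0, (0.05, 0.49), does not reproduce: the continuity-corrected score interval for 4/20 is (0.066, 0.443). Section 9.0 states no target response rate, alpha or power, so there is no power figure to reproduce.

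**Inputs.**
- 20 patients, at least 4 responses, null rate 5%, 30% loss before SBRT, 30% not assessable later: all from Section 9.0.
- True response rate of 20%: an assumption, set at the go threshold.
- Share of naive patients among the NSCLC enrolments: not given, so both extremes are shown.

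**Step 1. Patients reaching SBRT if accrual stops at 20 enrolled.** The 30% loss can apply only to patients who start MK-3475 on trial.
- All naive: 20 × (1 − 0.30) = 14.
- All with prior anti-PD-1 therapy: 20. Section 5.2.3 enrols these only if a suitable SBRT target exists.

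**Step 2. Chance of meeting the rule.** With X binomial(n, p), P(X ≥ 4) = 1 − Σ C(n,k) p^k (1−p)^(n−k) over k = 0 to 3. At p = 0.20:
- n = 20: 1 − (0.0115 + 0.0576 + 0.1369 + 0.2054) = 0.589.
- n = 14: 1 − (0.0440 + 0.1539 + 0.2501 + 0.2501) = 0.302.

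| Reaching SBRT | P(≥4) at 20% | P(≥4) at 5% | 4/n |
|---|---|---|---|
| 20 | 0.589 | 0.0159 | 20.0% |
| 14 | 0.302 | 0.0042 | 28.6% |

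A count of 4 is thus a stricter rule with fewer patients. If the team applied the 20% instead, it would need 3 of 14, with a false-go risk of 0.030 and a 0.552 chance of success at 20%. The operating characteristics shift either way.

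**Step 3. The later 30%.** It applies under both closing rules: 20 × 0.7 = 14 assessable under Section 9.0, and 14 × 0.7 = 9.8 under 5.2.1 with all naive. It is therefore not an effect of the conflict, and the like-for-like comparison is the one in step 2.

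**Step 4. Replacement of SBRT starters.** Suppose a fraction d of starters is replaced, none of them would respond, and they leave the denominator. A true rate of 5% among all starters becomes 0.05/(1 − d) among the 20 counted. The values of d are assumptions; the documents give none.

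| d | Rate among those counted | P(≥4 of 20) |
|---|---|---|
| 0 | 5.0% | 0.016 |
| 2% | 5.1% | 0.017 |
| 5% | 5.3% | 0.019 |
| 30% | 7.1% | 0.050 |

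**Step 5. Sections 5.8 and 5.2.3 side by side.** Section 5.8 covers both phases and has no DLT exception; 5.2.3 states this replacement for phase 1b only and has one. The overlap is narrow. Item 2 of 5.8 covers only non-toxicity stops, and 5.2.3 already stops SBRT for grade 3 or greater events attributed to radiation. What remains is mainly a DLT attributed to MK-3475 alone, followed by a stop for another reason.

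**The case against.** The strongest reply is that the plan as a whole points to counting SBRT patients. Section 9.0 replaces 12-month responders. Section 5.2.3 says of a patient with unresolved events before SBRT that "the patient will be removed from the study and replaced". Section 5.8 replaces anyone without a completed fraction, and the trial summary sizes the study by patients completing SBRT. On that view 5.2.1 is one loose sentence. This is fair as to intent, but the sentence is the operating instruction for closing accrual in the design section, and replacement cannot happen once accrual has closed.

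Three stronger readings are tempting, and the documents do not support them.
- *Three competing filling rules.* Section 5.8 is a replacement rule that can supplement either closing rule. Only 5.2.1 and 9.0 conflict.
- *The rule would rest on about 10 patients, with a 0.12 chance of success.* That figure adds the later 30% loss, which arises under either rule, and assumes every patient is naive, although Sections 5.2.1 and 5.2.3 also admit NSCLC patients after prior anti-PD-1 therapy.
- *Early failures are removed from the analysis.* No section says that replaced phase 2a patients leave the denominator. The examples in 5.8 are refusal and intercurrent illness, and patients who stop for toxicity after a first fraction are not replaced. SBRT is 1 to 5 fractions scheduled within 15 days, so high replacement rates look unlikely.

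A reader might also note that the stated interval fits 3/15 (0.053, 0.486) and infer a planned denominator of 15. The documents do not say how the interval was obtained, so that inference is not available.

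**Conclusion.** The point stands as a conflict between Sections 5.2.1 and 9.0 over when NSCLC accrual closes. Under the literal 5.2.1 rule, about 14 to 20 patients would reach SBRT instead of 20, and the chance of at least 4 responses at a 20% response rate would be 0.30 to 0.59 instead of 0.59. The low end requires that all patients are naive and that Section 9.0's 30% is right. The 14 is an expected count, and it leaves out other losses before SBRT, such as no suitable target or unresolved toxicity. The 20% rate is assumed.

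The undefined denominator is a secondary gap. If replaced starters are dropped and would not have responded, the response rate is biased upward. The false-go risk moves from 1.6% to 1.7–1.9% with 2–5% replaced, and to 5.0% at an extreme 30%. The true size is unknown and probably small. The DLT mismatch between 5.8 and 5.2.3 is real but narrow.

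**What to change.** 1. In 5.2.1, replace the count of 20 enrolled with Section 9.0's rule, made concrete: NSCLC accrual closes when 20 NSCLC patients, phase 1 included, have received at least one SBRT fraction. This is the threshold already used in item 1 of 5.8. Use the same words in 9.0.
2. State in 9.0 that all of these patients form the phase 2a response denominator, with non-assessable patients counted as non-responders, even if a further patient is enrolled under item 2 of 5.8.
3. Reconcile item 2 of 5.8 with 5.2.3, both on the phase it applies to and on patients who have had a DLT.

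With 20 patients fixed in this way, the rule has an exact one-sided false-go risk of 0.016 at 5% and a 0.589 chance of success at 20%.

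**Cost.** Protocol and SAP wording. The reported response rate may be slightly lower because patients with partial SBRT stay in. Total NSCLC enrolment exceeds the literal 5.2.1 cap, up to about 29 if all are naive (20/0.7 = 28.6), each receiving a first MK-3475 course. Section 9.0 already implies that number.

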5.2.3 Stereotactic Body Radiation Therapy (SBRT)

Target Selection

Target selection for SBRT will occur after the patient develops progression of disease on the pre-SBRT treatment with MK-3475. For the Phase Ib portion, patients will be allocated to Arm A (Lung target) if the SBRT target overlaps the lung parenchyma, otherwise patients will be allocated to Arm B (Non-Lung target). Targets suitable for SBRT for all phases of the study must meet all of the following requirements. Melanoma and NSCLC patients with prior treatment on anti-PD1 therapy will only be enrolled if there is a suitable target. In NSCLC patients initiating MK-3475 as first protocol treatment, if there are no suitable targets for SBRT after the pre-SBRT MK-3475, the patient may be observed and interval re-imaging may be obtained at the discretion of the investigators. Patients who cannot be treated with SBRT within 12 weeks of the most recent infusion of MK-3475 will be taken off treatment and moved to survival follow up. Exceptions to the 12 week window may be allowed for individual patients at the discretion of the Principal Investigator. MK-3475 may be administered after progression has been determined while SBRT is planned. Additionally, target lesions:

1. Must not be located in the liver, small or large bowel
2. Treatment must be accomplished without exceeding any normal tissue dose limit, as defined in the report of the American Association of Physicists in Medicine, Task Group 101 report[55].

SBRT Planning

Patients will undergo CT simulation and treatment planning per standard practice. Patient immobilization should be sufficient to ensure minimal intra- and inter-fraction set-up error, and is otherwise left to the discretion of the treating radiation oncologist. For lung targets, a technique for motion management is required, which may include tumor tracking, respiratory gating, or 4D-CT simulation. The treating physician will define a planning target volume (PTV) to which the dose will be described, and which will be used to define local control or local failure. At least 90% of the PTV should receive 90% or more the prescription dose. All organs at risk within 5 cm of the PTV will be contoured, and dose-volume histograms produced. For all organs at risk contoured, dose limits will be followed without exception[55].

SBRT Treatment Administration

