12.1 Evaluation of Best Overall Response

The Best Overall Response is the best response recorded from the start of the treatment until disease progression/recurrence (taking as reference for progressive disease the smallest measurements recorded since the treatment started). For purpose of the primary endpoint of the study, the overall response will be measured during the post-SBRT MK-3475, in comparison to the most immediate pre-SBRT imaging.

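### Nothing requires an unirradiated lesion to have been progressing, so new shrinkage on MK-3475 alone can count toward the 4-of-20 rule

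*Combined protocol and SAP*

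**What the plan says.** Section 5.2.1 makes progression on anti-PD-1 therapy (irPD) the gateway to SBRT. It also accepts progression by RECIST but not by irRC where the investigator judges that the drug will bring no further benefit. Both are judgements about the patient, not about a named lesion. MK-3475 may continue while SBRT is being arranged.

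Section 5.2.3 has the target chosen after that progression: "Targets suitable for SBRT for all phases of the study must meet all of the following requirements". The requirements listed are an anatomic exclusion and normal-tissue dose limits. Neither concerns which lesion grew. Entry (section 5.1) needs at least two measurable sites and sets no progression status for the second.

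After SBRT, section 5.2.1 states: "For the purpose of measuring response, the irradiated lesion will no longer qualify as measurable disease". Section 12.0 repeats this. For the primary endpoint, section 12.1 says that "the overall response will be measured during the post-SBRT MK-3475, in comparison to the most immediate pre-SBRT imaging". Section 12.0 also allows a scan taken just after SBRT as the baseline, if that is the more recent.

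Section 9.0 gives the decision rule: "If 4 of 20 patients (20%) in the NSCLC expansion cohort develop a partial or complete response to post-SBRT MK-3475", the strategy merits further study. The reference rate of under 5% is a presumption, which the plan words as "It is therefore presumed that the expected ORR without SBRT in this population" and ties to the fact that drug could be continued past RECIST progression in the first course. The one retreatment figure behind it comes from an anti-CTLA4 series of 31 melanoma patients who had earlier responded, in whom "re-induction with antibody resulted in a response in 13% of patients". The plan goes below that figure because some of those patients may have had pseudoprogression.

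**The concern.** The set of lesions that shows progression and the set that is scored for response are not the same. Progression is read on all disease, including the lesion that then becomes the SBRT target. Response is read on what is left. A patient with one growing lesion and others still shrinking on MK-3475 can pass from the first set to the second. Once the growing lesion is irradiated and removed, only drug-sensitive disease remains to be measured.

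The phase 2a question (section 3.0) is whether SBRT can induce a response to MK-3475 in patients who progressed on it. Lesions that the drug is still shrinking do not test that. The argument for a rate below 5% deals with pseudoprogression and says nothing about mixed response. The trial has one arm, so no comparator would show the difference, and section 9.0 plans no analysis by the pre-SBRT course of the unirradiated lesions. At stake is whether four responses in 20 can be read as evidence about SBRT.

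**Working it through.** **Inputs from the documents.** n = 20, threshold r = 4, reference rate p0 = 0.05 as the upper edge of the presumed range (all section 9.0). Two rates give context: about 20% of unselected NSCLC patients respond to first MK-3475 treatment (section 4.6), and 13% responded in the retreatment series (section 9.0).

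**The plan's own figures.** 4/20 = 20%, as stated. The accompanying statement, "The 95% confidence interval will be (0.05, 0.49) by using one-sample proportion test with continuity correction", does not reproduce for 4/20: the continuity-corrected score interval is (0.066, 0.443). The stated limits match 3/15, which gives (0.053, 0.486). That is a separate matter and nothing below uses the interval.

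**Step 1: the rule when the presumption holds.** With X ~ Bin(20, 0.05),

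P(X ≥ 4) = 1 − (0.3585 + 0.3774 + 0.1887 + 0.0596) = 0.016.

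**Step 2: sensitivity to the background rate.** Setting p in place of 0.05 for all 20 patients, P(X ≥ 4) is 0.047 at 7%, 0.058 at 7.5%, 0.133 at 10% and 0.257 at 13%. The rule is strict only if the rate without SBRT really is about 5% or less.

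**Step 3: a mixture.** Assume that m of the 20 are mixed responders whose remaining lesions reach a new CR/PR on drug alone with probability q, that the other 20 − m respond at 5%, and that SBRT adds nothing. Then

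P(≥ 4) = Σ_j P(Bin(m, q) = j) × P(Bin(20 − m, 0.05) ≥ 4 − j).

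Example, m = 4 and q = 0.10: 0.6561 × 0.0070 + 0.2916 × 0.0429 + 0.0486 × 0.1892 + 0.0036 × 0.5599 + 0.0001 × 1 = 0.028.

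| q (assumed) | m = 2 | m = 4 | m = 6 |
|---|---|---|---|
| 10% | 0.022 | 0.028 | 0.037 |
| 15% | 0.028 | 0.045 | 0.068 |
| 20% | 0.035 | 0.065 | 0.109 |
| 30% | 0.050 | 0.120 | 0.225 |
| 40% | 0.068 | 0.193 | 0.374 |

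The documents give neither m nor q. The table shows a range and does not estimate either.

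**Step 4: what scoring mixed responders as failures would cost.** If they stayed in the 20 but could never count, only 20 − m patients could supply the four responses. At a true rate of 20% the chance of passing falls from 0.589 to 0.499, 0.402 and 0.302 for m = 2, 4 and 6. At 30% it falls from 0.893 to 0.835, 0.754 and 0.645.

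**The case against.** The strongest reply has four parts.

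- **The baseline is reset.** Response is measured from a scan around SBRT, so a PR already reached, or stable disease, scores as stable. This stands. A reader might infer that any continuing MK-3475 response counts toward the four. Sections 12.0 and 12.1 do not support that, because only fresh shrinkage to CR/PR counts. It does not close the gap, since ongoing shrinkage can reach a new PR. MK-3475 may continue up to SBRT, and the pre-SBRT visit in section 7.3 lists no new scan. Shrinkage in that interval is therefore also credited unless a scan just after SBRT becomes the baseline.
- **The progression requirement screens out many mixed responders.** This also stands. Irradiating the only growing lesion is permitted, but not every patient with one growing lesion qualifies. The RECIST-only route requires a judgement of no further benefit, which fits poorly with other lesions that are clearly shrinking. How often growth in one lesion yields irPD cannot be settled from the documents.
- **The larger probabilities need high response rates.** Values of q of 30–40% exceed the plan's own 20% for first treatment. A subgroup picked out by shrinking lesions could exceed 20%, but no section says so. The range has to include 10–20%, where the chance is 0.022–0.109.
- **The stakes are modest.** This is a 20-patient, single-arm phase 2a trial, and the plan says openly that no historical control exists. That lowers the urgency, but the 4-of-20 rule is still what the plan uses to decide.

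**Conclusion.** The gap is real and its size is unknown. The sections together allow the only growing lesion to be irradiated and removed from measurement while the remaining lesions, none of which need have been progressing, supply the response. The under-5% reference rate was not argued for that situation. If SBRT adds nothing, the chance of a favourable result rises from 0.016 to between 0.022 and 0.374, depending on assumed values (2 to 6 mixed responders in 20, drug-alone CR/PR rate 10–40%, all other patients at 5%).

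Three stronger readings go too far. The upper figures are not a forecast, because no section supports m = 6 or q = 40%. Dropping the irradiated lesion from measurement is not itself an error, since the endpoint concerns systemic response. Nor do the documents require mixed responders to be scored as failures: that would cost considerable power (step 4), and it would discard patients whose stable unirradiated lesions shrink after SBRT, which may be the effect sought. What is missing is the information needed to tell these cases apart, and that is cheap to collect.

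**What to change.** At target selection, record on the CRF, from scans already in hand, the pre-SBRT change in each lesion that will remain measurable. Classify each patient by a threshold fixed in advance: at least one unirradiated lesion growing or new, or all stable or shrinking.

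Keep the 4-of-20 rule on all 20 patients. Add to sections 9.0 and 12.1:

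- a pre-specified report of CR/PR by this status;
- a sensitivity count restricted to responses in patients with at least one progressing unirradiated lesion;
- a statement that a favourable result resting on the other patients is not evidence of an SBRT-induced response.

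Treatment, eligibility, target choice and sample size are unchanged. The cost is SAP and CRF wording and the use of one earlier scan per patient, which for some patients treated with anti-PD-1 before entry must be retrieved from outside. The sensitivity count may also be less favourable than the main one.
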